We will approach this analysis in two ways. In both approaches, the numerator will be the number of patients who report cessation at six-month follow-up calls. In our primary analysis, we will use an intent-to-treat analysis in that we will include all practices (regardless of whether they actually use the intervention) and will include all smokers who are referred (the same denominator used in H1) regardless of whether they GO to the website. This represents a conservative assessment since we assume that many patients will not GO, and for the purposes of analyses, we will assume that these patients will not have quit. The most conservative analysis would be to use the total number of smokers seen in the practices as the denominator. However, we will not know this number exactly. Our exit cards give an estimate but we do not have a continuous measure of total smokers.

As a secondary analysis, we will assign the denominator as the number of patients who GO to the website. For this secondary analysis, consistent with current guidelines for smoking cessation trials, we will assume that patients who are lost to follow-up, including those who GO and do not agree to follow-up, are smokers.

We have assumed a control cessation rate of 17% among those with completed cases (follow-up complete) in the control group based on a range of completed case and intent-to-treat evaluations of prior internet smoking cessation interventions (Table 11). For the purposes of power calculations, we estimate

**Table 11:** Six-month cessation anticipated among completed cases, those who go to the website, and those referred from 80 practices.

	Six-month cessation among Completed Cases*†		Cessation among those who GO		Cessation among those who are referred‡ (Primary Analysis)	
	n/N	Proportion	n/N	Proportion	n/N	Proportion
Intervention	120/456	26%	120/760	16%	120/1920	6%
Control	20/120	17%	20/200	10%	20/960	2%

\* Completed Cases are those with completed six-month telephone surveys  
 † Assumes 60% follow-up among those who GO (see Table 8 for number who go per practice) and assigns not abstinent to those without follow-up  
 ‡ Assumes those who are referred and do not go are **not abstinent**, based on estimates of those referred from Table 8 multiplied by the number of practices

a 9% difference in cessation among those with completed cases in the intervention group. Those who do not agree to follow-up will be considered smokers. The intent-to-treat cessation rates are calculated as the sum of the completed case rate (the proportion who quit among those who

complete follow-up), and the rate among those that do not agree to follow-up (assigned as 0% cessation). We conservatively have anticipated that 60% of website participants will agree to follow-up. Thus, we anticipate an intent-to-treat cessation rate among those who go to the website of 15% in the intervention group (See Table 11). Based on this rate we have also calculated the more conservative assessment needed for our primary analysis, assuming that all those patients referred who do not GO are not abstinent.

The prevalence of tobacco cessation will be assessed at six months. Secondary dependent variables for H3 include reports of prolonged cessation, the number of quit attempts, and change in readiness to quit. Models will be constructed treating the number of quit attempts both as a continuous variable and as a Poisson variable. We will conduct additional analyses for quit attempts and change in stage.

Analyses for H3: We will first test the hypothesis for the main outcome (quit rate) and will conduct H3 at the patient level. Because we are comparing rates in all instances between intervention and control practices, we will use a two-group chi-square test of equal proportions to test the statistical difference between the quit rates. Due to the different referral mechanisms and the implications of referral for the providers, we expect that there may be differences in the characteristics of referred smokers between study groups. For instance, it is entirely possible that only those smokers who express a high readiness to change will be referred in the

Principal Investigator/Program Director (Last, First, Middle): DPBRN c/o [name]

control practices, while smokers in the intervention practices will be referred less selectively. To address this we will use a GLM with a logit link to model tobacco cessation by treatment assignment adjusted for readiness to change as entered into the website by the patient. Clustering by practice will be accounted for by employing generalized estimating equations as in our other analyses. We will do several multivariable analyses with separate models for overall quit rate, quit attempts, and change in stage. Patient and practice level variables will be used for adjustment in a similar manner to that described for H1. As an additional covariate, initial stage of change will be used to adjust models where the dependent variable is quitting or attempts.

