Cotinine biochemical verification: In 2002, the SRNT Subcommittee on Biochemical Verification published recommendations and evidence to aid the decision-making in choosing biochemical verification. This article divided studies into clinic-based trials (usually with less than 500 participants) where misclassification is higher and the need for biochemical verification is high and participation in biochemical verification is also high, versus population-based studies where misclassification is low and biochemical verification is less needed, and is in fact less feasible (with non-response rates up to 70%). In planning the study, we feel that HI-QUIT is closer to a clinic-based trial. The connection to the clinical microsystem makes this study more intense than public health interventions and may change the demand characteristics. To increase participation rates for the mailed salivary cotinine, we will provide an additional incentive of \$50 for completing this sample. However, we acknowledge that not all patients may complete cotinine validation by mail. For patients who self-report quitting at six months, but fail to return their cotinine saliva sample, we will use their self-report data, acknowledging that those who do not return their cotinine sample will be more likely to mis-report cessation. We will carefully assess for differential misclassification comparing intervention and control. First, we will compare participation rates for returning the cotinine sample by intervention and control. Next, we will assess self reported cessation among those that do and do not return the cotinine sample (comparing intervention and control). Finally, we will compare the misclassification rates among those that did return the sample (again intervention vs. control). If differences are detected, this would represent a case of non-ignorable missing data. Using these rates, we will conduct sensitivity analyses to assess the impact of differences in participation and misclassification on our main outcome and use pattern mixture approaches to assess how much our main analysis might change.

**D9. Analysis Plan:** For each practice, HI-QUIT is available for 20 months (see Figure 3, section D1). We plan to assess the impact of the intervention throughout this interval.

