Secondary analysis: Our primary approach does have the potential for errors resulting from lost, damaged, or mis-used “information prescription” pads in the control. This would result in a differential misclassification in the control as compared to the intervention group. As much of this error would underestimate the control denominator, it would still provide a conservative estimate. However, it is true that the inherent difference in the intervention and control creates a difference in the assessment of the denominator. Thus, as a secondary analysis and as safeguard against these error sources, we will repeat the analysis using the number of patients who GO as the outcome, with careful adjustment for *patient volume, proportion of smokers, and rates of referral as assessed by the exit cards at discrete time points*. This will allow us to check for consistency of results. The secondary analysis for the number who GO will use linear regression to model the number of patients per practice who go to the website by treatment assignment adjusted as above, where the test of H2 will be the significance of the coefficient for treatment assignment.

**Hypothesis 3: The proportion of smokers who are referred who QUIT at six months will be larger among intervention compared with control because of the additional connectivity of HI-QUIT.**

Data Definitions for H3: The main dependent variable for H3 is the dichotomous outcome of patient tobacco cessation (quit). The primary independent variable is assignment to intervention or control group. We have designed a patient-level analysis around point prevalence cessation based on the following question: “Do you currently smoke cigarettes (smoked even 1 puff in the last 7 days)?”

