For patients referred by hygienists using refer to quit, patient consent is layered and matched to the risk and burden to the patient. Patient consent is not obtained at chairside after they agree to be enrolled. At this level of participation, only patient email is collected. Intervention patients will receive emails after being referred to the intervention website by providers. To minimize risk, the emails will only contain a reminder to go to the website, but will not identify the purpose of the website. No personal health information will be in the emails. Because risk is low and it is not feasible to obtain informed consent without changing the processes of care themselves, we will not obtain informed consent at this level (similar to prior Fax-to-Quit studies).

If patients choose to log onto the web-based system, they will be asked to complete an online consent process where they agree to specific line items (agree to allow us to track their use of the site, agree to follow-up) by online check boxes verified with a username and password they create. If they agree, they will provide telephone numbers for follow-up. If they do not wish to participate in follow-up, they can use the online system without providing additional identifying information. Because participation is again optional, and because requiring written consent would likely greatly decrease use of the online system, we will not obtain written informed consent at this phase. Once the patient is called for follow-up, we will complete a verbal consent procedure for participating in the interview. If the patient reports smoking cessation, we will obtain written informed consent when the specimen is collected. Thus, signature documentation is only obtained for the subset of patients for whom biologic specimens are obtained. This layered procedure has been used in prior studies including DTC.Net and the NCI-funded Smoking Coach study referenced in the application.

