#### For Phone Interviews (Follow-up assessment of website participants to assess smoking cessation (H3):

Research assistants will obtain verbal consent to participate in the brief telephone survey. For quality assurance of data collection, a ten percent sample of telephone surveys will be audiotaped. The selected patients will also be asked if they are willing to be audiotaped. If the patient declines to be taped, they will be allowed to participate in the interview without the audiotape.

Patients who have quit at six months will be asked if they agree for us to mail them a saliva test kit for a salivary cotinine sample. If they consent, a collection tube from Salimetrics and instructions for use will be sent. The patient will mail the collection tube directly to the lab in a postage-paid envelope.

Risks to patients also include the burden of completing the exit interviews and follow-up surveys. We will provide a small compensation to offset the effort of participating in the follow-up telephone interviews and cotinine validation. Patients may certainly benefit from the training their providers have received in the form of more appropriate counseling.

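### The second cotinine check in D8 is uninformative as written, because kits go only to patients who already report quitting, so no planned check shows how non-returners differ from returners

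*Protocol*

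**What the plan says.** Section D8 (Main Evaluation Measures, the paragraph on cotinine verification) accepts that some patients who report quitting will not send the sample back, and fixes how they are counted: "For patients who self-report quitting at six months, but fail to return their cotinine saliva sample, we will use their self-report data". It adds that such patients are more likely to misreport.

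It then lists three checks for differential misclassification:

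1. Return: "First, we will compare participation rates for returning the cotinine sample by intervention and control".
2. Self-report by return status: "Next, we will assess self reported cessation among those that do and do not return the cotinine sample (comparing intervention and control".
3. Misclassification among those who returned the sample, by arm.

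If differences appear, D8 treats the missing samples as non-ignorable. It plans sensitivity and pattern-mixture analyses on the impact of differences in participation and misclassification.

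Section E (Human Subjects) says who gets a kit. Under the heading on phone interviews: "Patients who have quit at six months will be asked if they agree for us to mail them a saliva test kit". Earlier in the same section: "If the patient reports smoking cessation, we will obtain written informed consent when the specimen is collected". The self-report in question is the seven-day item of Table 10, "Do you currently smoke cigarettes (smoked even 1 puff in the last 7 days".

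**The concern.** Check 2 compares groups on the variable that selected them. A patient is asked for saliva because he or she reported quitting, so the later comparison of self-reported quitting by return status has nothing left to vary.

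Check 1 counts tubes, and check 3 looks only inside the returners. Check 2 is the one place where the plan looks at how non-returners differ from returners. The plan counts non-returners as quit while expecting them to misreport more often, so this is where some evidence would be most useful. At stake is how far the H3 quit rates rest on unverified reports, and whether that dependence differs by arm.

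**Working it through.** **Inputs**

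- Kit eligibility: a report of quitting at the six-month call (section E).
- Anticipated quitters among completed cases: 120/456 intervention and 20/120 control (Table 11). The denominators reproduce as 760 × 0.60 = 456 and 200 × 0.60 = 120; the proportions are 26.3% and 16.7%, printed as 26% and 17%.
- Sample return rate *r*: the protocol gives none for this trial. **Assumption:** 30% to 90%. The low end matches the non-response of up to 70% that D8 mentions for population-based studies. D8 places this trial nearer the clinic-based kind, so 30% is pessimistic.

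**Reading A: a non-returner was asked for a sample and did not send it.** This is how D8 itself describes non-returners. With *Q* quitters in an arm, returners number *Qr* and non-returners *Q*(1 − *r*), and all of them reported quitting:

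- returners: *Qr* / *Qr* = 100%
- non-returners: *Q*(1 − *r*) / *Q*(1 − *r*) = 100%

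At *r* = 50% the four cells are 60/60 and 60/60 (intervention) and 10/10 and 10/10 (control). No return rate within the range changes this, and neither would different rates in the two arms.

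**Reading B: a non-returner is any completed case without a sample**, including self-reported smokers who were never asked. With *N* completed cases:

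- returners: still 100%
- non-returners: *Q*(1 − *r*) / (*N* − *Qr*)

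| Assumed return | Intervention non-returners | Control non-returners |
|---|---|---|
| 30% | 84/420 = 20.0% | 14/114 = 12.3% |
| 50% | 60/396 = 15.2% | 10/110 = 9.1% |
| 70% | 36/372 = 9.7% | 6/106 = 5.7% |
| 90% | 12/348 = 3.4% | 2/102 = 2.0% |

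Each entry is fixed by *Q*/*N* (the arm's quit rate) and *r* (check 1). At equal return, the gap between arms only restates the difference in quit rates. With 70% return in intervention and 50% in control, the figures are 9.7% and 9.1%, so the gap almost closes although nothing about misreporting has changed.

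**Consequence for D8's rule on detected differences.** Under A, check 2 can never show a difference. Under B, returners and non-returners differ widely by construction. Neither result bears on whether non-returners misreport more.

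**Patients affected.** Quitters counted on self-report alone number 140 × (1 − *r*): 98 at 30% return (84 + 14), 70 at 50%, and 14 at 90% (12 + 2).

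**The case against.** The best defence is that the sentence is loose and not wrong. It says cessation will be assessed and names neither a rate nor a denominator. Two readings would give figures that vary.

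- **Verified and unverified cessation over the H3 denominators.** At 50% return this gives 60 unverified quitters of 1,920 referred against 10 of 960. That is useful to report, but it combines the quit rate with check 1 and does not describe how non-returners differ.
- **Prolonged cessation**, which D8 and D9 say will be collected. This could vary by return status, but D8 does not say that it is the measure meant.

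One may also say that such detail belongs in a statistical analysis plan. Adding detail could be left there, but the protocol already states this check, and its own rule for offering kits empties it.

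A reader might infer three stronger things, and the protocol supports none of them.

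- **That the check cannot be computed.** It can; the result simply carries no information.
- **That it will always show no difference, and so reassure falsely.** This holds only under reading A. Under reading B there is a large built-in difference. Even under A, an analyst who sees 100% in every cell should recognise the cause, and D8 says openly that it expects more misreporting in non-returners.
- **That the sensitivity analyses lose one of their inputs.** D8 ties them by name to participation and misclassification, which are checks 1 and 3. Both remain usable.

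**Conclusion.** The point holds in a limited form. Check 2 is uninformative under either definition of non-returner: 100% in all four cells, or values fixed by the arm's quit and return rates. This follows from the kit rule in section E and needs no numerical assumption. The illustrative counts rest on Table 11 and on assumed return rates.

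Checks 1 and 3, the primary H3 analysis, its denominator and the sample size are untouched, and the sensitivity analyses can still be run. What is lost is the only planned description of how unverified quitters differ from verified ones. Somewhere between 14 and 98 of about 140 anticipated quitters would fall in that group over the assumed range. It is worth correcting because the correction is cheap, but it does not threaten the trial's main result by itself.

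**What to change.** **Replace check 2.** Among self-reported quitters only, and by arm, describe returners and non-returners on data the protocol already collects: level of addiction, past quit history and type of tobacco use (Table 9), readiness as entered on the website (D9, analyses for H3), and prolonged cessation reported at the call. Every patient who reaches the six-month call came through the website, where the smoker profile is collected.

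**State the range for the planned pattern-mixture analysis.** Vary the misreporting rate in non-returners separately by arm, from the rate seen in returners up to 100%, where every non-returner counts as a smoker. As an illustration, at 50% return in both arms and before any correction for disconfirmed returners, the upper end moves the quit rates among those referred from 120/1,920 = 6.3% and 20/960 = 2.1% to 60/1,920 = 3.1% and 10/960 = 1.0%.

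Do not predict misreporting in non-returners from a model fitted to returners. That would assume equal misreporting given the covariates, against D8's own expectation. It would also rest on few events: 50% return leaves 70 returners, 10 of them control, and an assumed 10% to 20% disconfirmed gives 7 to 14 events in all, 1 to 2 in control.

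**Cost.** One sentence of D8 to reword, one to add, and a small table. There are no new data, contacts or samples. The limitation is size: with about 20 control quitters expected, the comparison is descriptive and should not be tested formally.

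### Cotinine non-return is called non-ignorable only if arm differences are detected, although the protocol already concedes that non-returners mis-report more; the sensitivity analyses should be stated to run regardless

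*Protocol*

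**What the plan says.** The relevant text is the cotinine paragraph of Protocol section D8, Main Evaluation Measures.

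- For patients who report a quit at six months but send back no sample, "we will use their self-report data, acknowledging that those who do not return their cotinine sample will be more likely to mis-report cessation". They therefore enter the H3 numerator as quit.
- Three comparisons between arms are then promised without condition. The first is "First, we will compare participation rates for returning the cotinine sample by intervention and control". The second looks at self-reported cessation by whether a sample was returned. The third compares misclassification among those who did return one.
- Next comes "If differences are detected, this would represent a case of non-ignorable missing data".
- The sentence after that reads "Using these rates, we will conduct sensitivity analyses to assess the impact of differences in participation and misclassification on our main outcome", and goes on to pattern-mixture approaches for gauging how far the main analysis might change.

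No test, significance level or threshold is given for a detected difference. No planned cotinine return rate is given either. The paragraph cites non-response of up to 70% in population-based studies, but places this trial nearer the clinic-based type. Section E says of the kits: "Patients who have quit at six months will be asked if they agree for us to mail them a saliva test kit". The comparisons of return and misclassification therefore rest on self-reported quitters only.

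**The concern.** Missing data are non-ignorable when being missing is related to the unobserved value. The protocol grants this when it says of its own rule, "acknowledging that those who do not return their cotinine sample will be more likely to mis-report cessation". The property holds within each arm and needs no difference between arms. Making the label depend on a detected arm difference contradicts that premise.

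The practical question is what happens when no difference is seen. The sentence on sensitivity analyses follows the conditional one directly and concerns the impact of differences. A team following the text could reasonably run the three comparisons, find nothing significant and stop. H3 would then rest on unverified self-report, with an admitted bias left unexamined. Two features make this more than a matter of wording: few quitters are expected in the control arm, and an arm comparison cannot reveal misreporting that is equal in both arms.

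**Working it through.** **Inputs.** Table 8 (rounded): 19 and 5 patients per practice GO. Section D5: 40 practices per arm. Section D9 and Table 11: 60% follow-up; completed-case quit rates 26% and 17%; referred denominators 1920 and 960. Section D10: 48 and 24 referrals per practice; ICC 0.017. Return and misreporting rates are not in the protocol and are assumed below.

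**1. Table 11 quitter counts.** Practices × GO × follow-up × quit rate:
- Intervention: 40 × 19 × 0.60 × 0.26 = 118.6 (stated 120).
- Control: 40 × 5 × 0.60 × 0.17 = 20.4 (stated 20).

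Both reproduce. Reported rates are 120/1920 = 6.25% and 20/960 = 2.08%, a difference of 4.17 points and a ratio of 3.0.

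**2. Power if detection means a two-sided 0.05 test.** This is exact binomial enumeration with clustering ignored. Each range runs from the Fisher test to the uncorrected chi-square.

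| Comparison (intervention v control) | n | Power |
|---|---|---|
| Return 50% v 70% | 120 v 20 | 31-38% |
| Return 70% v 50% | 120 v 20 | 38-42% |
| Return 50% v 60% | 120 v 20 | 9-13% |
| Misreporting 25% v 10% among returners, 60% return in both arms | 72 v 12 | 7-13% |
| Misreporting 10% v 25%, same returners | 72 v 12 | 28-37% |

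By normal approximation, 80% power from a 50% control return rate needs a gap of about 31 points.

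Section D10 notes that one year is assumed but 20 months are available. Scaling by 20/12 gives about 200 v 33 quitters, and chi-square power for 70% v 50% return becomes about 62%.

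**3. Equal misreporting in both arms.** True quits = reported × (1 − share unreturned × share of those false).
- 50% unreturned, 30% false: factor 0.85, so 102/1920 − 17/960 = 5.31% − 1.77% = 3.5 points.
- 70% unreturned, 50% false: factor 0.65, so 78/1920 − 13/960 = 4.06% − 1.35% = 2.7 points.

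The ratio stays 3.0 in both cases. The risk difference is overstated by 0.6 and 1.5 points, and no arm comparison would show it.

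**4. Unequal return.** Assume 50% v 70% return and 40% of non-returners false in both arms.
- Intervention: 120 − 60 × 0.4 = 96, or 5.0%. Control: 20 − 6 × 0.4 = 17.6, or 1.8%. The difference is 3.17 points, an overstatement of 1.0 point.
- With 50% return in both arms instead: 96 and 20 − 10 × 0.4 = 16, difference 3.33 points. So about 0.83 of the 1.0 point is equal misreporting and about 0.17 comes from unequal return.

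**5. Effect on the H3 test.** Design effects: 1 + 47 × 0.017 = 1.799 and 1 + 23 × 0.017 = 1.391. Effective sizes: 1920/1.799 = 1067 and 960/1.391 = 690. Pooled two-proportion z:
- As planned (120 v 20): z = 4.07.
- 50% v 70% return, unverified counted as smoking (60/1920 v 14/960): z = 2.20, p about 0.03.
- 30% v 50% return, unverified counted as smoking (36/1920 v 10/960, or 1.9% v 1.0%): pooled p = 0.0155, SE = √(0.0155 × 0.9845 × (1/1067 + 1/690)) = 0.00603, z = 0.00833/0.00603 = 1.38, p about 0.17.

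**The case against.** The strongest reply is that the protocol does not gate anything. The if-clause governs only the non-ignorable label. The next sentence says the sensitivity analyses will be conducted, using rates that exist whatever a test shows. This stands as far as it goes: the dependence is inferred from adjacent sentences, and a sponsor who always meant to run the analyses loses nothing by saying so. It does not rescue the label, which contradicts the protocol's own concession however the following sentence is read.

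A reader might infer that H3 could be reported with no check at all. The document does not support that, since all three arm comparisons run unconditionally. Only the sensitivity and pattern-mixture analyses could be skipped.

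The power figures depend on a 0.05 test that the plan never names, and each takes one comparison alone although three are planned. Both are fair limits. They do not make detection a sound trigger: the undefined threshold leaves the choice to be made after the data are seen, and the second comparison appears to add little, because only patients reporting a quit are sent a kit.

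A reader might also take the 1.0-point overstatement in step 4 as the cost of a weak test, or conclude that H3's significance is in doubt generally. Neither follows. Most of that point is equal misreporting. On the odds-ratio scale of the adjusted model the example moves only from (120/1800)/(20/940) = 3.13 to (96/1824)/(17.6/942.4) = 2.82. At the planned effect the test survives that example, and survives counting all its unverified quits as smoking.

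Finally, the protocol already offers an incentive for returning the sample and discloses the self-report rule. The exact grid of misreporting values can properly be left to the SAP.

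**Conclusion.** The concern holds in limited form. Section D8 concedes the condition that makes the missing cotinine results non-ignorable, then makes that status depend on a detected arm difference. On the natural, though not explicit, reading, the sensitivity and pattern-mixture analyses hang on the same condition. If detection means a two-sided 0.05 test on Table 11's one-year counts, power is about 31-42% for a 20-point gap in return and about 7-13% for misreporting of 25% v 10% among returners at an assumed 60% return. It is higher but still limited over 20 months. Equal misreporting escapes the condition entirely and inflates the risk difference while leaving the ratio unchanged.

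At the planned effect the consequence is mainly for the size of the effect. Significance could be lost if returns are low, as in the assumed 30% v 50% case, or if the true effect is smaller than planned. All return and misreporting rates here are assumptions. This is a change that should be made, but it does not undermine the primary definition.

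**What to change.** Delete the condition on detected differences. State that, whatever the three arm comparisons show, the primary H3 result will be reported beside:

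1. an analysis counting unverified self-reported quits as smoking, with all referred patients as denominator; and
2. the pattern-mixture analysis over a range of misreporting among non-returners, including values equal in both arms and values that differ by arm. The range may be fixed in the SAP.

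A separate analysis of verified quitters only is not needed: with the referred denominator it is the same as (1).

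The primary definition is unchanged. The cost is a sentence or two and a few extra model runs. The downside for the sponsor is that a fragile result would be visible.
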